# 4.4.4 **Patient Dry Mouth Questionnaire**

Subjects will be asked to complete a questionnaire about their dry mouth symptoms (see Appendix 24.7) once during Screening Stage II and on Days 0, 14, 28, 42, and 56. Completing the questionnaire can take up to 15 minutes.

# 4.4.5 Sjögren's Disease Activity Index

The clinician will use the Sjögren's Disease Activity Index to assess disease activity in each subject (see Appendix 24.9) once during Screening Stage IIand on Days 0, 14, 28, 42, and 56.). This index review takes up to 30 minutes for the clinician to complete.

# 4.4.6 **Parotid Fill Volume Determination**

Most subjects are expected to have a fill volume of less than 1 mL per parotid gland. To make certain that the subjects can be cannulated and determine whether the parotid fill volume is less than 1 mL, each subject will undergo cannulation and fill volume assessment at Stage I screening as follows:

- 1. The parotid duct will be gradually dilated with increasing probe diameter sizes starting at 0000.
- 2. After the dilations, a soft catheter will be placed over the 000 probe and inserted into the duct.
- 3. The probe will be slowly removed, and a syringe filled with 1.5 mL saline will be attached on the catheter and the saline slowly injected.
- 4. The injection will be terminated when the fill volume is completely injected, up to 1 mL.

This assessment takes up to 20 minutes to complete.

# 4.4.7 Collection of Laboratory Tests

# 4.4.7.1 Phlebotomy and Urine Tests

- Participants will have a 30mL blood sample drawn through phlebotomy and provide a urine specimen. The laboratory at the NIH Clinical Center will be the central laboratory for all routine laboratory parameters (hematology, chemistry, and urinalysis). Routine laboratory tests will be collected at Screening Stage I, Screening Stage II, and on Days 0, 28, and 56, and, if clinically indicated for procedures at the Safety Follow-up assessment. The following hematology, chemistry, and urine parameters will be assayed. Complete blood count with differential and platelets.
- Inflammatory markers: erythrocyte sedimentation rate (ESR) and C-reactive protein (CRP).
- Clotting parameters: PT, PTT (required 7 days before each parotid biopsy)

- Chem panel: albumin, alkaline phosphatase, alanine aminotransferase, aspartate aminotransferase, blood urea nitrogen, calcium, chloride, carbon dioxide (bicarbonate), creatinine, glucose, potassium, sodium, total bilirubin, and total protein.
- Serum amylase.
- Pregnancy test (urine or serum) (24 hours prior to technetium, MRI or parotid gland biopsy)

Other laboratory tests of immunologic function will be collected on Days 0, 28, and 56. Immunologic assessments will include:

- antinuclear antibodies, extractable nuclear antigens
- rheumatoid factor
- C3 complement, C4 complement
- immunoglobulin (Ig)A, IgG, and IgM.A

In addition, on Days 0 and 28, blood samples will be drawn for measurement of plasmaconcentrations of dexamethasone prior to randomized irrigation treatment at Days 0 and 28 to obtain a pre-irrigation baseline measure and post-irrigation at 75 ( $\pm$ 15) minutes after irrigation. Laboratory assessment collections can take up to 20 minutes to complete.

Blood will be collected at Day 0, Day 28, and Day 56, 24 mL total, to be used for these research tests: The serum and peripheral blood mononuclear cells will be isolated and stored under appropriate conditions. To determine the molecular mechanism of action of dexamethasone in this study, the following investigations are planned: Characterization of the fluid secretion mechanism after irrigation with corticosteroids, through assays of activities at the following levels: single protein (single-channel recording); subcellular; cellular (monitoring organellar and single-cell current, Ca2+, and pH); and tissue (use of volume changes as reported of fluid secretion by acinar cells and the micro-dissected sealed-duct system to measure all ductal secretory and signaling functions). Immunofluorescence will also be used to assay localization and expression levels of all key acinar and ductal transporters.

## 4.4.8 Minor Salivary Gland Biopsy

Some subjects may require an MSG biopsy during Stage I screening to confirm eligibility if their last MSG biopsy was >7 years at the time of screening. Medication to numb the lower inside lip

will be administered and a small incision will be made to extract salivary glands. The area will be closed with stitches. This procedure can take up to 30 minutes to complete.

#### 4.4.9 Ultrasound-guided Parotid Core Needle Biopsy

Ultrasound-guided core needle biopsy of the right parotid gland will be obtained at Screening Stage II and Day 56 to evaluate inflammation (including focus score). Using ultrasound, the parotid gland will be visualized, a small incision will be made at the base of the jaw and a needle will be guided into the parotid gland to retrieve a biopsy tissue sample. Two cores will be submitted in a fixative to pathology to be processed for regular histological analysis. The remaining cores will either be placed in cell culture medium or be snap-frozen for further processing. This procedure can take up to 45 minutes to complete. If the baseline measurements are not informative for the study as deemed by the PI, comparable readings at Day 56 will not be performed.

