#### 4.3 Screening

Subjects who have been diagnosed with primary SS in Protocol 84-D-0056 will be eligible for participation. Subject consent will be obtained before any study activities or procedures. Screening will be conducted up to 12 weeks before Day 0 in two stages (Stage I & Stage II) to minimize procedures for subjects who do not meet initial salivary flow criteria. Multiple visits will be needed to complete the screening portion of the protocol.

Stage I screening assessments will be done within 6 weeks prior to Stage II and will include vital signs, medical and medication history, review of concomitant medications and evaluation of salivary flow. If salivary flow meets eligibility criteria the following additional Stage I procedures will be done: physical examination, pregnancy testing, routine clinical laboratory tests, and review of previous MSG biopsy. If the subject continues to meet eligibility for study participation according to the preceding assessments, she will undergo parotid saline irrigation and fill volume measurement. If an MSG biopsy has not been performed within 7 years of screening and an MSG biopsy needs to be performed, the saline irrigation and fill volume measurement will occur after the results of the MSG biopsy are obtained, as the final assessment of Screening Stage I.

Screening Stage II will be done within 6 weeks prior to Day 0 and will include vital signs, administration of the dry mouth questionnaire (Appendix 24.7), Sjogren's Disease Activity Index (Appendix 24.9), laboratory blood assessment for baseline values, magnetic resonance imaging, and technetium scan, and a parotid core needle biopsy. For the Screening Stage II, the pregnancy test must be within 24 hours before the technetium and MRI scans (for subjects of childbearing potential). A CBC with differential and platelets, PT, and PTT will be done within 7 days before each of the ultrasound-guided core needle parotid biopsies. All study visit procedures are detailed below in section 4.4 as well as a description of the approximate time to complete each procedure.

[figure not shown]
We will accept results of imaging procedures done elsewhere if completed within 3 months of enrollment (screen-stage 1 visit).

Subjects who randomize and receive one study treatment (Day 0) and take an excluded concomitant medication (immunosupressants) may re-screen. They will not have screening MRI, Technetium scan, or parotid biopsy procedures repeated.

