6	Baseline ultrasound-guided core needle biopsy will be performed at least 14 days before Day 0. Follow-up biopsy will be performed after the technetium and magnetic resonance imaging scans on Day 56.									
7	Complete blood count with differential and platelets, Chem 14, erythrocyte sedimentation rate, C-reactive protein, and amylase. Prothrombin time and partial thromboplastin time will be obtained at Stage II screening and Day 56. The completed blood count with differential and platelets, prothrombin time, and partial thromboplastin time must be done with 7 days before ultrasound-guided core needle biopsy of the parotid. Clinical laboratory tests will be performed at the Safety Follow-up only if clinically indicated.									
8	Antinuclear antibodies, antibodies to extractable	nuclear antigens, rheuma	toid factor, C3 complement	nt, C4 complement, imm	nunoglobulin (Ig)A,	IgM, and IgG.				
9	Two samples will be obtained: one prior to rando treatment.	mized irrigation treatme	nt of the parotid glands (ba	aseline) and the other 7	5 ( $\pm$ 15) minutes afte	r irrigation				
10	Performed as final step of Stage I, when subject h	as otherwise qualified for	or the study.							
11	Performed as final step of Stage II, when subject	has otherwise qualified	for the study.							
12	2 Performed if a minor salivary gland biopsy is needed based on criteria in Section 3.2. Must be conducted and evaluated prior to any other procedures and activities associated with Stage II screening.									
13	3 On Days 0 and 28, obtained prior to irrigation treatment.									
14	Assessed via telephone. Clinic visit scheduled, if	deemed necessary based	l on medical need or per su	ıbject request.						
15	Performed only if clinic visit deemed necessary pe	er telephone interview.								

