## 4.4.12 Parotid Treatment Irrigation of the parotid duct (dexamethasone or saline)

Treatment irrigation will follow saliva collection on Days 0 and 28. Subjects will be randomized to receive dexamethasone irrigation in either the left or right parotid gland, with placebo (normal saline) administered in the opposite gland. Both the subject and the assessor of salivary flow will be blinded as to which parotid gland receives which treatment. Randomization of parotid glands within subjects will be done by the Pharmaceutical Development Service Department of the Pharmacy at the NIH. The person assessing salivary flow will not be involved in performing the irrigation.

Information on the dexamethasone formulation used in the study is provided in the dexamethasone package insert in Appendix 24.5. The Clinical Center Intravenous Admixture Unit at the NIH will prepare vials containing placebo or dexamethasone. The placebo vial will contain 0.9% sodium chloride for injection. The dexamethasone vial will contain 2 mg of dexamethasone sodium phosphate for injection diluted with 0.9% sodium chloride for injection. Solution will be drawn from the vial into a 1 mL syringe. The volume of each irrigation syringe will be determined by the parotid gland filling volume and specified in the medication order. The total volume will be between 0.5 and 1 mL. All vials will be labeled with the following information:

- Dexamethasone or saline.
- Subject name.
- Subject study number.
- Date dispensed.
- The words "Right parotid" or "Left parotid".
- Dose (2 mg).
- Volume.

Dexamethasone and saline placebo will be dispensed by designated Pharmacy Department staff according to their SOPs. The Pharmacy Department staff will document receipt and dispensation of study drug on drug accountability logs. The dispensation records will identify the name, lot number, and expiration date of the drug, as well as the identification number of subject and the quantity of drug dispensed to each subject. Accidental or intentional destruction of study drug will also be documented. All records will be available for inspection by the clinical trial monitor. Unused study drug will be discarded in the clinic post-procedure per standard NIH drug destruction policy.

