#### 6.2 **Concomitant Medication Contingencies**

During the period of the study, subjects will not be allowed to use the following medications: human or murine antibodies, rituximab, warfarin, heparin, immunosuppressants (e.g., methotrexate, leflunomide, azathioprine, cyclophosphamide, systemic cyclosporine, systemic corticosteroids, and intra-articular corticosteroids), or any experimental drug. If it is necessary to prescribe one of these medications, the subject may participate in subsequent treatments, without repeating baseline MRI, NM Scan or Parotid Biopsy, after a washout of 3 months for immunosuppressants Additionally, subjects must refrain from the use of salivary stimulants within 24 hours prior to each study visit. If a subject enters the study on a stable dose of antimalarial drug or NSAID, the dose should not be increased during the study. All effort should be made to maintain stable dosing of other concomitant medications, including saliva substitutes.

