#### 7.5 Ultrasound-guided Parotid Gland Core Needle Biopsy

Subjects will undergo a core needle biopsy of the right parotid gland during the Screening Period and on Day 56. Ultrasound guidance will be used to localize the biopsy site within the gland, and local anesthetic will be administered to minimize pain during the procedure.

Several recent publications have described ultrasound-guided core needle biopsy of the parotid gland as a low-risk alternative to open surgical biopsy. Available published data indicate that the procedure is relatively simple and safe to perform and yields sufficient tissue for accurate pathologic diagnosis. The diagnostic accuracy (mainly for tumors) in 319 patients was 96% to 100%, with only 5 (1.6%) reported complications. Four of these complications were hematomas, most of which did not require any intervention. One patient with metastatic squamous cell carcinoma developed a parotid fistula after biopsy. The main risk of an open biopsy of the parotid is injury to the facial nerve (controlling motor function on the ipsilateral face); however, no such complication has been reported with ultrasound-guided core needle biopsy of the parotid, no SAEs were reported. One subject had an infected hematoma that responded promptly to antibiotics. The most common complaint was mild to moderate pain or discomfort at the site of the biopsy, which responded to simple analgesics. Other possible risks with the core needle biopsy are allergic reactions to the local anesthetic, bleeding at the biopsy site, and local infection; however, such events are rare.

Subjects in this study will be screened for a history of bleeding disorder and have a CBC with differential and platelets, PT, and PTT before each core needle biopsy. Any discomfort, pain, or swelling at the biopsy site will be treated with acetaminophen or more potent analgesics as needed. If facial nerve injury should occur, the subject will be referred to an appropriate subspecialist for care to minimize the damage. Subjects will be asked to sign a separate surgical consent form prior to the biopsy procedure.

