#### 10.1.4 Demographic and Baseline Characteristics

Demographic and baseline characteristics will be summarized in tables. Continuous demographic and baseline variables will be summarized as means, medians, SDs, minimum values, and maximum values. Categorical demographic (e.g., race) and baseline variables will be summarized as frequencies and percents. Baseline variables pertaining to the parotid gland will be summarized by their assigned treatment. Differences between parotid glands by side of the body (right or left) and assigned treatment will be estimated with 90% confidence intervals.

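### Does biopsying only the right parotid mean the salivary flow models must contain a term for gland side?

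*Protocol*

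**What the plan says.** Two sections restrict the core biopsy to one side. Section 4.4.9 states "Ultrasound-guided core needle biopsy of the right parotid gland will be obtained at Screening Stage II and Day 56", and section 7.5 says the same: "Subjects will undergo a core needle biopsy of the right parotid gland during the Screening Period and on Day 56".

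On timing, a footnote to Table 4-1 states "Baseline ultrasound-guided core needle biopsy will be performed at least 14 days before Day 0", and section 4.3 states "Screening Stage II will be done within 6 weeks prior to Day 0". The first biopsy therefore usually falls 2 to 6 weeks before Day 0. For subjects who re-screen after taking an excluded drug the gap is longer. Section 4.3 says of them "They will not have screening MRI, Technetium scan, or parotid biopsy procedures repeated", and section 6.2 lets them continue "without repeating baseline MRI, NM Scan or Parotid Biopsy, after a washout of 3 months for immunosuppressants".

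On allocation, section 4.4.12 states "Subjects will be randomized to receive dexamethasone irrigation in either the left or right parotid gland". No left/right balancing of the list is mentioned.

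On analysis, section 10.1.5 models the change from Day 0 to Day 56 with treatment, a random subject effect and Day 0 flow. Section 10.1.6 adds study day. Neither names gland side. Section 10.1.4 does use side, at baseline only: "Differences between parotid glands by side of the body (right or left) and assigned treatment will be estimated with 90% confidence intervals".

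**The concern.** Every right gland has tissue removed before Day 0 and no left gland does, and the primary contrast is between the two glands of the same woman. The protocol thus builds a systematic left/right difference into the unit being compared, records side, and then leaves it out of the model.

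If a biopsied gland were still recovering, or deteriorating, between Day 0 and Day 56, its change in flow would differ from that of the other gland for a reason unrelated to treatment. That difference would enter the error term. With an uneven split, such as dexamethasone on the right in 11 of 16 subjects, it would also move the estimate in that particular trial. The sample size is set at 80% power, so there is little to spare.

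**Working it through.** **1. Can the missing term cause bias or a false positive?** Write the paired difference (dexamethasone minus saline) for subject *i* as D = τ + s·β + e, with s = +1 if the right gland gets dexamethasone and −1 if the left does. β is the right-minus-left difference in change. Side is randomised, so E(s) = 0 and the mean of D has expectation τ whatever β is. In simulations with β up to 0.0896 mL/min, one-sided type I error without a side term was 0.048–0.052 under simple randomisation. At a forced 8/8 split it was at or below nominal within simulation error, for example 0.036 at β = 0.04. There is no bias on average and no inflation.

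**2. What part of a biopsy effect reaches the endpoint?** Day 0 flow is measured after the first biopsy. An effect of the same size on Day 0 and Day 56 subtracts out of the change score, so β is only the part that changes between those days.

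**3. Planned precision.** Inputs from Table 10-1: SDs of change 0.0168 (saline) and 0.0906 (dexamethasone), correlation 0.15. From 10.2: n = 16, 80% power, one-sided 0.05.

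SD of D = √(0.0168² + 0.0906² − 2·0.15·0.0168·0.0906) = √(0.000282 + 0.008208 − 0.000457) = 0.0896 mL/min.

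The planned n of 16 can be neither reproduced nor refuted, because the protocol gives a 40% increase but no baseline flow. With a noncentral t on 15 df, 16 subjects have 80% power for 0.0584 mL/min. This difference is used below; it equals 40% of a baseline of 0.0584/0.40 = 0.146 mL/min. The Day 0 covariate is ignored.

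**4. Power without a side term.** β is not in the documents, so a range is assumed.

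| Assumed β (mL/min) | 8/8 split | Simple randomisation |
|---|---|---|
| 0 | 80.0% | 80.0% |
| 0.005 | 79.9% | 79.9% |
| 0.01 | 79.7% | 79.6% |
| 0.0168 | 79.1% | 78.8% |
| 0.02 | 78.7% | 78.3% |
| 0.04 | 74.8% | 73.4% |

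**5. Power with a side term (14 df), whatever β is.** The cost depends on the covariance. Section 10.2 assumes an unstructured one, under which the low-variance saline glands estimate side cheaply. Section 10.1.5 names only random subject effects. In that plain model each subject contributes one paired difference, so the analysis reduces to least squares on D, with the variance multiplied by 1/(1 − s̄²), where s̄ is the mean of s.

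| Split | Unstructured covariance | Plain random-subject model |
|---|---|---|
| 8/8 | 79.8% | 79.8% |
| 9/7 | 79.7% | 79.2% |
| 10/6 | 79.5% | 77.5% |
| 11/5 | 79.0% | 74.3% |
| 12/4 | 78.3% | 69.2% |
| Average, simple randomisation | 79.4% | 77.2% |

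A split of 11/5 or worse has probability 0.21 under simple randomisation.

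**6. Break-even.** The term begins to pay at β of about 0.009 mL/min with an 8/8 list. Under simple randomisation it begins to pay at about 0.012 with the unstructured covariance and about 0.025 with the plain model. The last is 0.025/0.0584 = 43% of the detectable drug effect. Below these values the term loses power, by at most 80.0 − 77.2 = 2.8 points on average.

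**The case for a change.** The best case for the concern is that the protocol does not leave its primary model open. It names the outcome, the random effect and one covariate with a reason, and the analysis plan might simply copy this. With a balanced list and the term included, the most that can be lost is 0.2 points, while about 5 points are protected at β = 0.04 (79.8% against 74.8%). An unbalanced list cannot be repaired afterwards: at 11/5 the estimate shifts by (11 − 5)/16 = 0.375 of β. Table 4-1 also places the Day 56 biopsy after the scans without placing it relative to saliva collection, so an acute effect on Day 56 flow is not ruled out by the text.

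This arithmetic is right, and a statistician could reasonably choose the term with a balanced list. It does not show that anything in the plan is wrong. A side effect of 0.04 is 68% of the detectable drug effect and more than twice the whole saline-gland SD of change. Section 7.5 describes the biopsy as low-risk, with mainly mild to moderate pain, and mentions no effect on flow. The first biopsy precedes Day 0 by at least 14 days. The chance shift at 11/5 is part of the random error that the one-sided 5% test already covers. The Day 56 ordering leaves a question open, but even an acute right-gland effect would fall on a randomised side. Naming one covariate in a protocol does not prevent the analysis plan from adding another, and left/right balance is a detail of the pharmacy's randomisation specification.

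Right-only biopsy does make the focus-score comparison a between-subject one. That is a different question, and a side term in the flow models would not touch it.

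**Conclusion.** The concern does not hold. Its facts are correct: only the right parotid is biopsied, and no side term is listed. Randomisation of side keeps the flow comparison valid without one, and the change score removes any stable biopsy effect. What remains is a possible loss of precision of 0.3 to 0.4 power points at an assumed side effect of 0.01 mL/min and about 5 to 7 points at 0.04, set against a cost of 0.2 to 2.8 points for the term if there is no side effect.

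These figures rest on the Table 10-1 SDs and correlation, 16 evaluable subjects, a detectable difference of 0.0584 mL/min, no allowance for the Day 0 covariate, and side effects that are assumed throughout. Which choice is better depends on an effect the documents give no reason to expect and on a covariance structure that 10.1.5 does not fix. That makes the side term a modelling preference suited to the analysis plan, which may exist but is not shown. The protocol needs no change on this point.

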#### 4.4.10 Technetium Scan

During Screening Stage II and on Day 56, subjects will have a dynamic technetium scan of the salivary glands to assess gland function. For this scan, they will receive 7 millicuries (mCi) technetium 99m (99mTc) pertechnetate intravenously, followed immediately by imaging over the head and neck region with a gamma scintillation camera. Subjects will be imaged for 60 minutes, followed by several 2- to 5-minute spot views. At 40 minutes post-injection, they will have 1 mL citric acid solution administered orally. A urine or serum pregnancy test must be done within 24 hours prior to the procedure as applicable. This procedure can take up to 2.5 hours to complete. If the baseline measurements are not informative for the study as deemed by the PI, comparable readings at Day 56 will not be performed.

